**Which Committee will review this protocol?**

The Clinical Research Committee - (CRC)

## Protocol Body

### 1.0 Objectives

1. Primary
  - 1.1 Determine whether transfer of myeloma specific immunity is enhanced by vaccinating donors prior to donor lymphocyte infusion with an id-specific vaccine.
2. Secondary
  - 2.1 To determine the rate of partial response (PR) and complete response (CR) in patients receiving donor lymphocytes (recipients) from an id-specific vaccinated donor.
  - 2.2 To determine the GVHD rates after donor lymphocyte infusion from an id-specific vaccinated donor.

### 2.0 Background

#### Current Results with Allografting in Myeloma

Although high dose chemotherapy and autologous transplant has improved the outcome for myeloma patients (1), most patients with myeloma will eventually relapse after high-dose therapy and autologous transplantation and die of their disease. Allogeneic transplantation has been explored in younger patients as a mean for overcoming stem cell contamination with myeloma cells and with the hope of obtaining a graft-versus tumor effect that could eradicate the malignant clone. A large report from the European Transplantation Registry showed disappointing results for patients undergoing allogeneic transplantation. Median survival was only 18 months, and the transplant-related mortality (TRM) was prohibitive at 41% (2,3). The HOVAN group recently published the results of its initial experience using T cell depleted myeloablative bone marrow transplant in patients with HLA identical sibling donors. After initial therapy with VAD regimen, patients younger than 55 with an HLA-identical sibling underwent allogeneic transplantation with cyclophosphamide (Cy) and TBI (N=47) or Cy/TBI plus idarubicine (N=5). All patients received ex-vivo T-cell depleted transplantation with the goal of reducing TRM. Eleven percent of patients developed grade III acute graft-versus host disease (GVHD), and 30% developed chronic extensive GVHD. Transplant-related mortality was 34%; median OS was 25 months from the time of transplantation and was significantly inferior to survival for same patients in other arms of the trial (47 months). Despite T-cell depletion, TRM remained elevated and a graft-versus myeloma effect was not apparent in this trial (4). Thus high transplant-related mortality precludes the use of myeloablative conditioning regimens for myeloma patients.

Allogeneic stem cell transplantation with reduced-intensity or non-myeloablative conditioning regimens has been attempted in patients with multiple myeloma. Table 1 summarizes the results of various phase two trials that have been published over the past few years. (5-11) Relapse was the most important cause of treatment failure, particularly for patients with chemorefractory disease. However, the observation that a small percentage of refractory myeloma patients can achieve long term disease control support further exploration of reduced intensity allografting as a curative strategy for myeloma. Patients receiving a non ablative allograft as part of their initial therapy, have been reported to have TRM of less than 15%, however, relapse is a common cause of treatment failure with 33% of patients receiving reduced intensity allografts as part of their initial therapy.

**Table 1: Results Of Nonmyeloablative Transplantation.**

Reference	N	Regimen	RR (CR)	Agyhd > Grade II	CGVHD	TRM	DFS	OS @ 2years
5	22	FM	72% (32)	46%	27%	40%	19% @ 2 years	30%
6	45	Mel 100 FM/TBI	61% (31)	42%	58%	38%	13% @ 3 years	36%
7	29	FM	45%	52%	51%	21%	33% @ 2 years	60%
8	41	Fbu ATG	50% (25)	40%	51%	17%	NR	62%
9	64	FM/ATG	90% (45)	39%	47%	23%	38% @ 2years	55%
10	31	Mel FM/TBI	61%	58%	NR	30%	31% @ 2 years	31%
11	54	TBI	52%	39%	46%	15%	55% @ 2 years	78%

RR: Response Rate. CR: Complete Response. aGVHD: acute Graft-Versus-Host Disease. cGVHD: chronic Graft-Versus-Host Disease. TRM: Transplant Related Mortality. DFS: Disease-Free Survival. OS: Overall Survival. FM: Fludarabine/Melphalan. TBI: Total Body Irradiation. ATG: Anti-Thymocyte Globulin. NR: Not Reported.

Non-myeloablative transplantation for myeloma is increasingly being explored as part of a tandem strategy, in which patients are treated with autologous transplantation followed by planned allogeneic transplantation. Maloney et al, recently published their experience with fifty-four patients receiving an autologous transplantation with melphalan (200 mg/m^2), and after a median of two months, low-dose total body irradiation (single fraction 2Gy) followed by stem cell transplantation from an HLA-identical sibling. Estimated 2-year overall survival and disease-free survival were 78% and 52%, respectively (11). This, although encouraging, these results show that myeloma relapse will continue to be a major cause of treatment failure post-allograft, treatment of relapse with donor lymphocyte infusion has been successful but only in a minority of patients. Therefore strategies aimed at enhancing the graft vs myeloma effect without increasing toxicity need to be developed.

#### **Donor Lymphocyte Infusions (DLI) for Myeloma**

Interest in allografting for myeloma increased due to the demonstration of a graft versus myeloma effect (GVM) demonstrated by responses to donor lymphocyte infusions. (12-16) Up to 50% of patients respond to DLI, including some with sustained complete remission; however, incidence of acute and chronic GVHD is elevated and limits the widespread use of this strategy (15). The results of the largest DLI series for myeloma are summarized in Table 2.

**Table 2: Results of Largest Donor Lymphocyte Infusion Series for Myeloma**

Reference	N	Response Rate CR+PR	GVHD ≥2 (>Grade 2)	Comments
13	27	52% (22+30)	56% (15%)	Primarily T cell depleted transplant recipients
14	25	44% (28+16)	48% (24%)	Only 3 responders without GVHD
15	54	52% (17+35)	46% (20%)	T cell depleted patients primarily
16	11	90% (54+36)	50%	CD8 depleted DLI

Thus, in myeloma graft versus tumor responses seem to correlate with GVHD, possibly due to the fact that myeloma associated antigens that have been shown to be targets for the GVM effect are also

expressed in other tissues (17). Therefore, one possible strategy is to divert the GVM effect towards targets that are expressed primarily in myeloma cells and not in other tissues. This could increase the therapeutic efficacy of donor lymphocyte infusions. Vaccination with myeloma specific antigens is such an approach.

### **Vaccination therapy for Myeloma**

Vaccination against tumor specific antigens could enhance the graft versus myeloma effect of donor lymphocyte infusions. Immunoglobulin (Ig) molecules are composed of heavy and light chains, which possess highly specific variable regions at their amino termini. These variable regions contain determinants (molecule shapes) that can themselves be recognized as antigens or idiotypes, and are patient specific. Thus the idiotypic determinants of the surface Ig of a B-cell lymphoma or myeloma can thus serve as a tumor-specific marker for the malignant clone.

Studies in experimental animals, as well as in man, have demonstrated that active immunization against idiotypic determinants on malignant B-cells can produce resistance to tumor growth in a number of syngeneic experimental tumor models, as well as specific anti-tumor therapy against established tumors (18-27). These results, taken together, provided the rationale for testing autologous tumor-derived idiotypic surface Ig (Id) as a therapeutic "vaccine" against human B cell malignancies. Furthermore, preclinical studies in subhuman primates demonstrated that optimal immunization with human lymphoma-derived Id required conjugation of the protein to an immunogenic protein carrier (keyhole limpet hemocyanin; KLH) and emulsification in an adjuvant (28).

Kwak et al immunized nine patients with B cell lymphoma with autologous idotype protein. These patients received no anti-tumor therapy during the time of the study. They were either in complete remission or in a state of minimal residual disease following conventional chemotherapy. In addition, three patients with rapidly progressive recurrent lymphoma were enrolled in a separate safety study; all three required re-institution of chemotherapy shortly after enrollment, did not complete the immunization series, and were not studied further. They received intramuscular injections of 0.5 mg of Id conjugated to KLH at 0, 2, 6, 10, and 14 weeks, followed by two booster injections at 24 and 28 weeks. The KLH carrier provided a convenient internal control for immunocompetence of the patients, and all patients demonstrated both humoral and PBMC proliferative responses to the KLH protein, with the exception of one patient, who demonstrated only the latter. Seven of the nine patients demonstrated either a humoral (n=2) or a cell-mediated (n=4) anti-idiotypic immunological response, or both (n=1) (29). Toxicity was minimal in all twelve patients. All patients experienced transient local reactions characterized by mild erythema, induration, and discomfort, without skin breakdown, at the injection s. Id immunization was associated with a mild elevation (less than twice the normal value) of serum creatine phosphokinase 24 hours after immunization in an occasional case. These results demonstrate that patients with B cell lymphomas can be induced to make sustained idotype-specific immune responses by active immunization with purified autologous tumor-derived surface Ig. They show that autologous Id, made immunogenic by conjugation to KLH, can serve as an immunogen (antigen) to elicit host immunological responses.

Similar clinical results were observed in multiple myeloma patients. At the University of Turin 12 patients with myeloma received high-dose chemotherapy and autologous stem cell transplantation followed by vaccination with Id-specific proteins conjugated to KLH and GM-CSF or IL-2 as immunoadjuvants (30). Id-specific T cell proliferative responses were documented in 2 patients, and a positive Id-specific delayed-type hypersensitivity reaction was observed in 8 of the 10 patients studied. Twelve patients with multiple myeloma were treated at Stanford University with high-dose therapy and peripheral blood stem cell transplantation followed by Id immunizations (31). Following transplantation patients received a series of monthly immunizations consisting of Id-pulsed autologous dendritic cells followed by subcutaneous (S.C.) boosts of Id conjugated to KLH. The administration of Id-pulsed DC and Id-KLH vaccines was well tolerated with patients experiencing only minor and transient side effects. Two of 12 patients developed an Id-specific, cellular proliferative immune response, and one of three patients studied developed a transient but Id-specific cytotoxic T cell response. Similarly, investigators at the University of Wales were able to generate dendritic cells from six patients with IgG myeloma, and the cells were pulsed with the

autologous Id (32). Id-specific responses were also observed. PBMC proliferative responses to Id were observed in five of the six patients following treatment. These initial trials demonstrate that the vaccination of patients was relatively safe and capable of producing Id-specific T cell responses.

Granulocyte-macrophage colony-stimulating factor (GM-CSF; sargramostim) has emerged as a promising adjuvant for idiotypic Ig antigen. Syngeneic mice (10 mice per group) were immunized with 50 mcg Id-KLH derived from the tumor either alone or in combination with GM-CSF mixed together with the antigen and administered subcutaneously. Three additional daily doses of GM-CSF were administered S.C. as close to the original of immunization as possible. Mice immunized with an irrelevant Id-KLH (4C5 IgM) served as negative controls for the vaccine. Two weeks after this single immunization, all mice were challenged with a single preparation of 38C13 tumor cells ( $5 \times 10^3$  cells i.p.) and followed for survival. The results demonstrate that the augmented survival benefit afforded by immunization with relevant Id-KLH alone can be significantly enhanced by the addition of GM-CSF at either the 100 or 10,000 unit dose. A curious but reproducible observation has been the loss of this protective effect at a higher dose of GM-CSF of 50,000 units (data not shown). These data suggest that GM-CSF may have a potent adjuvant effect in vivo for Id-KLH antigen, especially at relatively low doses (33).

Idiotype protein vaccine in combination with GM-CSF as an adjuvant was evaluated in 20 lymphoma patients in first clinical complete remission (34). GM-CSF administration was well tolerated with minimal side effects. Tumor-specific cytotoxic CD8+ and CD4+ T cells were found in 19 of 20 patients. This data seem to indicate that GM-CSF may be an essential component of this vaccine formulation's potency.

#### **Donor Vaccination with Idiotype-KLH vaccine**

Most vaccination protocols have attempted to vaccinate the patient against their own malignancy. Intuitively, however, this strategy has the main obstacle that the patients immune system has already failed to respond to the tumor in an effective manner. The availability of a vaccine derived from the immunoglobulin idiotype as a tumor-specific antigen, opened the opportunity to study the transfer of antigen-specific antitumor immunity from an immunized stem cell donor to the SCT recipient. Kwak et al have explored this strategy of transferring tumor idiotypic-specific immunity with bone marrow from specifically immunized donors in a preclinical murine model (35). The 38C13 B cell tumor is a carcinogen-induced C3H cell line, which both expresses and secretes idiotypic Ig both in vitro and in vivo. Thus, it can serve as a model for well differentiated B cell malignancies, such as lymphomas or myelomas. Mice serving as syngeneic marrow donors were immunized with tumor-derived Id protein or with a control immunoglobulin of matched isotype. Naive lethally irradiated recipients reconstituted with marrow from immune donors showed serologic tumor idiotype-specific immunity, as well as protection against subsequent lethal tumor challenge. The immunoprotective effect of immune marrow was also shown in the setting of combined donor and recipient immunizations. These results demonstrate the successful transfer of tumor antigen-specific immunity with immune marrow as a protective element and provide support for testing this approach in humans.

- 1) Will id specific donor vaccination translate into a skewing of lymphocyte repertoire to a more myeloma specific spectrum?
- 2) Is it possible to quantify the degree that myeloma specific immunity is enhanced by id-specific vaccination?
- 3) Do ex-vivo measures of id-specific immunity correlate with disease control?
- 4) Will id specific vaccination of donors prior to lymphocyte collection enhance the efficacy of donor lymphocyte infusions for myeloma patients not in remission after allogeneic transplantation without increasing the risk of GVHD.

### 3.0 Background Drug Information

#### **3-A Id-KLH Vaccine Myeloma Immunoglobulin Idiotypic Vaccine (NSC-678327, BB IND 5779)**

Availability - Individual Myeloma immunoglobulin are obtained from each patient and individual vaccine is prepared for each patient at the **GMP Facility of MDACC**.

Idiotypic Vaccine Preparation - Idiotypic vaccines are prepared using a recipient's idiotype protein. The patient-specific protein will be isolated from the recipient's plasma (via plasmapheresis), purified by protein A or anti-Hu IgA affinity chromatography, and covalently coupled to a keyhole limpet hemocyanin (KLH) as described in **Appendix G**. The preparation of the final vaccine product (myeloma idiotype protein conjugated with KLH) will be performed by **GMP Facility of MDACC**. Each batch of patient-specific vaccines will be produced according to Good Manufacturing Practices (GMP) standards and will be tested for sterility, endotoxin contamination, and general safety, prior to its use in any patient. The final vaccine product (myeloma idiotype protein conjugated with KLH) will be manufactured (and vialled) by **the GMP Facility of MDACC**. Each patient-specific vaccine will be labeled to include the following information:

- a) myeloma immunoglobulin idiotype vaccine: patient-specific lot
- b) final volume and concentration of vaccine product
- c) KLH and patient-specific immunoglobulin subtype
- d) storage conditions
- e) fill date
- f) patient identification (first name/last initial)

Storage and Stability - The final product is available as a solution containing 1.1 mls of conjugated protein diluted in sodium chloride 0.9% (NS). The solution is contained in a 1.8 ml insert inside a sterile vial. The final solution contains 0.5 mg/ml of KLH conjugated to 0.5 mg/ml of the patient-specific immunoglobulin idiotype protein. Intact vials are stored at -20° C.

Administration - The patient (recipient) and donor will receive 3 subcutaneous injections of the patient-specific vaccine preparation containing 0.5 mg of the myeloma protein at the protocol specified timepoints. Both individuals will receive GM-CSF as an adjuvant to the vaccine preparation. GM-CSF will be administered as a subcutaneous injection at a dose of 250 mcg/m^2 (rounded up to the nearest vial)

daily for four consecutive days (day 0-day 3).

Adverse events- described with Id-KLH vaccine administration include local reactions (erythema, induration, swelling and tenderness), fever, chills, rash, myalgias and arthralgias. Mild elevations in creatinine phosphokinase (CPK) have been observed. Fever and chills, associated with vaccine administration will be treated with acetaminophen and/or meperidine.

### **3-B Unconjugated KLH**

Availability – KLH according to GMP standards as described above, will also be vialled as a separate product by the MDACC GMP facility and will be supplied by the investigational pharmacy. This vialled product will be tested separately for sterility, endotoxin, and general safety, prior to its use in any patient. Each vial of KLH will be labeled to include the following information:

- a) Patient-specific lot
- b) Final volume and concentration of product
- c) Patient-specific immunoglobulin subtype
- d) Storage conditions
- e) Fill date
- f) Patient identification (first name/last initial)

Adverse events– The toxicities associated with the administration of unconjugated KLH are anticipated to be identical to those described with the Id-KLH vaccine. The safety issues regarding the injection of heterologous idiotype protein isolated from other patients' B-cell tumors have already been fully addressed in CC Protocol 96-C-0133 (NCI T93-0164; Id Vaccination in Previously Untreated Patients with Follicular Lymphoma) and are felt to be minimal, because of the highly purified nature of the protein. Briefly an immune response of any consequence to the isotype used as a negative control during the skin test is not likely, based on:

- a) Any immune response specifically directed against the idiotype (i.e., variable region) on the control idiotype protein is not likely to cross-react with host cells and is therefore not likely to be of any consequence.
- b) An autoimmune response against constant region or allotype determinants shared between the idiotype of patient's own tumor and that of the control idiotype is theoretically possible. However, no evidence of such autoimmune responses have been observed either in vivo or in vitro during the course of immunization of the normal donors so far treated or in the patients who underwent autologous transplantation. Furthermore, a safety precedent exists for immunizing patients with material derived from tumor cells from other patients. For example in attempting to develop immune responses against metastatic melanomas, patients were immunized with 1) intact melanoma cells: 2) shed antigens fractionated by detergent treatment and ultracentrifugation: 3) melanoma cells infected with vaccinia virus and melanoma cells freeze thawed and mechanically disrupted, all using a pool of allogeneic melanoma cell lines.

### **3-C Sargramostim (granulocyte-macrophage colony-stimulating factor; NSC - 613795; BB-IND 2632, Leukine)**

Availability - The GM-CSF to be used in this study is a glycosylated, recombinant human GM-CSF. This GM-CSF is an altered form of the native molecule; the position 23 arginine has been replaced with a leucine to facilitate expression of the protein in yeast (*Saccharomyces cerevisiae*). Manufactured by Immunex. GM-CSF will be provided by the protocol from a commercial source.

Storage and Stability - The GM-CSF is formulated as a white lyophilized cake and is provided in vials containing 500 mcg of the GM-CSF protein as well as 10.0 mg of sucrose, 40.0 mg of mannitol, and 1.2 mg of Tris (Trimethylamine). The unreconstituted material should be kept refrigerated at 2-8°C and is stable for at least eighteen months. Once reconstituted, the solution is stable for at least 24 hours at 2-8°C or at

18-25° C. Because the product does not contain a preservative, vials should be treated as unit-dose containers; reconstituted solution should be held at 2-8° C and discarded after no more than six hours. Do not freeze GM-CSF.

**Preparation** - To prepare a vial of GM-CSF for direct subcutaneous use, aseptically inject 1.0 ml of Sterile Water for Injection, USP, into the vial to dissolve the lyophilized cake. The diluent should be directed against the side of the vial to avoid excess foaming. Avoid vigorous agitation of the vial; do not shake. This yields a solution containing 500 mcg/ml.

**Administration** - The appropriate total dose is withdrawn into and administered from a plastic tuberculin syringe. The GM-CSF will be injected subcutaneously as close as possible to the Id-KLH injection. All GM-CSF doses for each patient will be administered by the nursing staff in the outpatient unit.

**Adverse events**- Toxicities described in patients receiving GM-CSF include: fever, chills, diaphoresis, myalgias, fatigue, malaise, headache, dizziness, dyspnea, bronchospasm, pleural effusion, anorexia, indigestion, nausea, vomiting, diarrhea, injection tenderness, urticaria, rash, pruritus, hypersensitivity reactions, bone pain, thromboembolic events, phlebitis, hypotension, peripheral edema, leukocytosis, thrombocytosis or thrombocytopenia, hepatic enzyme abnormalities, and bilirubin elevation. The first administration of GM-CSF has provoked a syndrome of dyspnea and hypotension within two hours after GM-CSF injection in a single patient receiving yeast-derived GM-CSF; this type of reaction has more frequently been observed in patients receiving GM-CSF produced in *E. coli*. One report of a vascular leak-like syndrome occurring after autologous bone marrow transplant in a patient receiving continuous IV (intravenous) infusion of GM-CSF has been recorded.

## 4.0 Patient Eligibility

### Recipient Criteria for Vaccine Production

1. Recipient for vaccine production: Patient with IgG1, IgG2, or IgG4 Multiple Myeloma who has received or is planning to receive an allogeneic progenitor cell transplant from a HLA compatible related donor (either 6/6 or 5/6 related donor).
2. Recipient for vaccine production: Have evidence of persistent or relapsing disease as demonstrated by persistent serum peak (by either standard protein electrophoresis, immune fixation or free light chain assays) or marrow infiltration. Serum peak must be greater or equal than 0.2 gm/dl and represent more than 70% of the specific immunoglobulin subtype. Patients who have adequate amount of monoclonal idiotype protein previously cryopreserved on prior departmental laboratory protocols are also eligible to be registered for vaccine production using the cryopreserved samples.
3. Able to sign written informed consent.
4. Age up to 70 years.
5. Zubrod PS  $\geq$ 2.
6. Have no serious organ dysfunction as defined by serum creatinine  $<$ 2.5 mg/dL, serum bilirubin  $<$ 3 x upper limit of normal, SGPT  $<$ 4 x upper limit of normal.
7. Negative donor infectious disease panel:
  - Hepatitis B surface antigen (HBsAg)
  - Anti-Hepatitis B core antibody (HBcAb)
  - Anti-Hepatitis C Virus antibody (HCV Ab)
  - Anti-Human Immunodeficiency Virus (HIV) antibody (HIV 1/2 type O Ab)
  - Anti-Human T cell lymphotropic Virus (HTLV) antibody (HTLV I/II Ab)
  - Rapid Plasma Reagen (RPR)
  - Cytomegalovirus antibody (CMV)
  - HCV/HIV Nucleic Acid Test
  - West Nile Virus Nucleic Acid Test
  - Sickledex
  - T Cruzi AB

Additional tests shall be performed as required to assess the possibility of transmission of other infectious or non-infectious diseases.

8. Negative serum Beta HCG test in a women with child bearing potential (not post-menopausal for 12 months or no previous surgical sterilization) and willing to use an effective contraceptive measure while on study. Mothers should not breastfeed during the study.

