#### **Exclusion Criterion**

1. Recipient with IGg3 Multiple Myeloma.

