## 6.0 Treatment Plan

### Idiotype Procurement

6.1 Recipient will undergo steady state plasmapheresis procedure to provide idiotype protein necessary to produce the vaccine. This is a standard procedure. Plasma (60-100 cc) from the plasmapheresis procedure will be sent to the MD Anderson Cancer Center GMP lab where it will be processed. The MDACC GMP lab will be responsible for producing the id-KLH conjugated vaccine according to the supplied standard operating procedure (see PDOL Appendices H and I). The vaccines will be kept in the GMP lab until requested. Alternatively vaccine can be produced using previously collected idiotype monoclonal protein collected on ongoing laboratory protocols and cryopreserved.

6.2 Donor will be vaccinated with an id-KLH vaccine 0.5 cc subcutaneously, once during weeks -8, -6, and -2 prior to donor lymphocyte collections.

The preferred site for the vaccine injection are the deltoid area (upper arm) and thigh. Sites should be alternated with each vaccine administration.

All donors will be observed in the clinic for two hours following vaccine administration. During the observation period, vital signs will be taken every 15 minutes during the first hour and then every 30 minutes during the second hour following vaccine administration.

6.3 GM-CSF 250 mcg/m^2 (dose rounded up to the nearest vial) S.C. will be given daily for four days (days 0-3) after each vaccine. All GM-CSF injections will be given in close proximity to the vaccination, as close to the exact site of injection as possible to ensure optimal recruitment of dendritic cells. The first dose of GM-CSF will be given by a nurse, and the remaining three doses will be given by the donor. Research staff will provide educational instructions regarding subcutaneous injection administration.

6.4 Recipient must meet the following criteria in order to receive the vaccine:

- Recipient to receive vaccine must be greater or equal than 3 months post allograft and with 5% or greater donor cell engraftment
- On a prednisone or prednisone equivalent dose of no more than 10 mg every other day at the time of registration, and with tacrolimus levels of <5 ng/dl or cyclosporine levels of < 100 ng/dl.
- Have no uncontrolled GVHD.

- Negative serum Beta HCG test in a woman with child bearing potential (not post-menopausal for 12 months or no previous surgical sterilization) and willing to use an effective contraceptive measure while on study.

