## **10.0 Statistical Considerations**

**Preliminaries.** This is a single-arm feasibility trial of Id Specific vaccinated DLI for treatment of multiple myeloma patients post allograft from a matched sibling donor who are not in CR or relapsing after transplant at least 3 months after stem cell transplant. The last myeloma therapy must be at least 3 weeks prior to entry. Labeling time of DLI as week 0, each donor will be vaccinated at weeks -8, -6, -2 and each patient will be vaccinated at weeks, 0, 4, and 8. Toxicity (TOX) will be defined as the event that the patient suffers grade 2, 3 or 4 GVHD or death within 6 months post DLI. The historical rate of TOX is 50% (54/107). The primary aim is to determine whether transfer of myeloma specific immunity is enhanced by vaccinating donors prior to donor lymphocyte infusion with an id-specific vaccine.

**Trial Conduct.** A maximum of 10 patients will be treated.

**Analysis of Myeloma Specific CTLs over time.** A generalized linear mixed model (Diggle, et al., 1998) will be fit to the longitudinal measurements of myeloma specific CTLs. For patient  $j = 1, \dots, 20$  at observation time  $t = -8, -6, -2, 0, 4, 8, 12$ , denote the myeloma specific CTL count by  $Y_{j,t}$  and covariate vector by  $Z_j$ . The model is given by

$$g\{E(Y_{j,t})\} = m + f_j(t) + b Z_j + \text{error}$$

where  $g$  is a suitable link function,  $m$  is the overall mean,  $f_j$  is a patient-specific function of  $t =$  time from day of DLI, accounting for the manner in which  $Y$  varies over time and includes a patient effect to account for correlation among the successive observations on each patient,  $Z_j$  is a component accounting for patient covariates with  $b$  is a covariate parameter vector, and "error" is the usual measurement of error.

Additional analyses of the final data will include analysis of survival times as functions of the treatments and patient prognostic covariates using an appropriate survival regression model determined by goodness-of-fit analyses.

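### Recipient criterion 5 is written as Zubrod PS ≥ 2, which on the usual scale excludes the fittest recipients, sets no limit on poor performance status, and runs opposite to the criteria beside it

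*Combined protocol and SAP*

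**What the plan says.** In Section 4.0, under the recipient criteria for vaccine production, item 5 is an inclusion criterion consisting only of Zubrod PS ≥ 2. It is a lower bound on the score, with no upper bound.

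Its neighbours are upper limits. Item 4 is "Age up to 70 years". Item 6 begins "Have no serious organ dysfunction as defined by serum creatinine" and requires creatinine below 2.5 mg/dL, bilirubin below 3 times the upper limit of normal and SGPT below 4 times the upper limit of normal.

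The only listed exclusion is "Recipient with IGg3 Multiple Myeloma". A second set of recipient conditions stands in Section 6.4, introduced by "Recipient must meet the following criteria in order to receive the vaccine". It covers time since allograft, donor engraftment, steroid dose and immunosuppressant levels, GVHD and pregnancy testing. Section 10.0 describes the population as post-allograft patients "who are not in CR or relapsing after transplant at least 3 months after stem cell transplant" and puts no restriction on performance status.

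**The concern.** On the usual Zubrod scale a higher score means a less able patient. A minimum score of 2 therefore turns away the ambulatory, active recipients and lets in those who spend most or all of the day in bed. Nothing in the objectives or background says the trial is meant for impaired recipients only, and the criteria on either side screen out higher-risk patients. The likeliest explanation is a reversed inequality.

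This is an operative rule. It decides who may be registered for an intervention whose main expected harm is GVHD and for which Section 10.0 quotes a historical toxicity rate of 50% (54/107). Followed literally, it exposes the frailest candidates and refuses the fittest. It would also make the treated group, at most 10 recipients, less like the patients behind that historical rate.

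**Working it through.** The plan gives no figure to reproduce. The check is to read item 5 against the scale, against its neighbours, and against the rest of the document.

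**1. What item 5 admits.** Assume the standard scale, with scores 0 to 4 for living patients and 0 the best.
- Score ≥ 2 admits {2, 3, 4} and refuses {0, 1}.
- If only the sign were reversed, the admitted set would be {0, 1, 2}. This is an illustration of what hangs on the symbol, not a proposed rule.
- The two sets share only score 2, so the direction of the sign decides eligibility for four of the five scores.

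**2. Direction of the adjacent criteria.**
- Item 4 (age): upper limit; excludes older patients.
- Item 5 (Zubrod PS): lower limit; on the assumed scale, excludes the more able patients.
- Item 6 (creatinine, bilirubin, SGPT): upper limits; exclude patients with organ dysfunction.

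Item 5 alone runs the other way.

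**3. Search for a correcting rule.** None of the following mentions Zubrod or performance status:
- the exclusion criterion (IgG3 myeloma only);
- Section 5.0, pretreatment evaluation;
- Section 6.4, conditions before the recipient is vaccinated;
- Section 7.0 B, recipient evaluations;
- Section 9.0, removal criteria;
- Section 10.0, including the toxicity monitoring rule.

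Item 5 is the only performance-status rule in the plan.

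**4. Consistency with the procedures.** Section 6.10 has recipients give themselves three of the four GM-CSF doses after each vaccine. Section 7.0 has them keep a diary, bring it to visits, and attend follow-up to 24 months. This suggests functioning outpatients but does not prove it.

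**5. Could the symbol be a reading error?** Other inequality signs read sensibly: the < signs in item 6, the ≥ in the CD3+ collection target in Section 6.5, and the ≥ in the GVHD column heading of Table 2. A single reversal introduced by text extraction is therefore unlikely, though possible.

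**6. Effect on the statistical design.** The monitoring rule in Section 10.0 depends on the prior, the 0.90 probability cut-off, the 50% reference rate and the numbers of patients and toxicities. Performance status enters none of these. The boundaries stand, and so does the table of operating characteristics, which is conditional on the true toxicity probability.

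**The case against.** The strongest objection is that everything rests on one character, recovered from a PDF by a program and appearing only once. The extracted text is visibly damaged elsewhere: one column heading in Table 1 garbles an abbreviation that the table's own footnote spells correctly. Nor do the documents say which way the Zubrod scale runs. Both caveats stand. They make checking the source the first step, but they do not remove the point, because the other inequality signs came through intact and the assumed scale direction is the standard one.

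Several stronger readings are tempting and are not supported.

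- *Extra early deaths would push the trial towards a 50% limit.* Section 10.0 defines TOX as "the event that the patient suffers grade 2, 3 or 4 GVHD or death within 6 months post DLI", so death counts there, but the 50% attached to that definition is a historical rate. The rule that uses 50% as a stopping reference counts only grade 2–4 acute GVHD within 6 months. A death without such GVHD adds nothing to it.
- *The effect is 10 percentage points per death.* Given "A maximum of 10 patients will be treated", one event is 1/10 of a full trial, but that holds for any event and does not measure this flaw. The documents give no performance-status distribution and no death rate by performance status.
- *Item 5 fixes performance status when the TOX clock starts.* It applies at registration for vaccine production, and item 1 admits patients who have not yet had their allograft. Section 6.4, the later check, has no performance-status condition. The link from item 5 to events after DLI is therefore indirect, and correcting item 5 alone would not govern status at infusion.
- *Staff already apply the opposite rule and are recording violations.* The documents say nothing about conduct on this point.
- *Reversing the sign gives the intended rule.* The documents show neither the intended direction nor the intended threshold.

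**Conclusion.** Item 5 is wrong as written and must be corrected. Read on the standard scale, it bars every PS 0–1 recipient, admits PS 3–4 without limit, contradicts the direction of items 4 and 6, and is corrected nowhere else. If it is applied literally, the trial registers only recipients with impaired performance status. That is a patient-safety concern in its own right, and it weakens comparison with the historical series.

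The size of that loss of comparability cannot be given, because the documents report no performance status for the historical patients. Sample size, stopping boundaries and operating characteristics do not change. The conclusion rests on two assumptions: that the standard Zubrod direction is meant, and that the extracted symbol matches the source.

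**What to change.** 1. Verify item 5 of the recipient criteria against the source document, to rule out a misread symbol.
2. If the symbol is as shown, reconcile the direction and threshold of item 5 with items 4 and 6 and with the population described in Section 10.0. The sponsor should confirm the intended cut-off; none is proposed here.
3. Correct the text of item 5, and state the direction of the scale so that the criterion can be read without assumption.
4. Check that the eligibility checklist carries the same rule.

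The cost is one line in Section 4.0 and a checklist comparison. No change is needed to the sample size, the monitoring rule or the analysis.
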